### 10.2.2 QUALITATIVE ANALYSIS

Qualitative data will be transcribed and analysed in NVivo, using both descriptive (e.g. understanding their experiences) and interpretive (e.g. interpreting them in cultural context) phenomenology approaches. Comparative analysis will also be carried out; this method allows data from different participants to be compared and contrasted. Deviant cases will be actively sought throughout the analysis and emerging ideas and themes modified in response.

## 10.3. DATA STORAGE

Data and all appropriate documentation will be stored for a minimum of 10 years after the completion of the study, including the follow-up period.

## 10.4. MONITORING

Both UK and Thai PIs are jointly responsible for data produced in this study and assurance of its quality. The LSHTM-based research fellow and Thailand-based research assistant will conduct data collection, management, curation, security and sharing during the lifetime of the grant.

The Chief Investigator will inform the sponsor should they have concerns, which have arisen from monitoring activities, and/or if there are problems with oversight/monitoring procedures.

# 11. REGULATORY ISSUES

## 11.1 ETHICS APPROVAL

This study is to be conducted according to the international standards of Good Clinical Practice (GCP) (International Conference on Harmonization guidelines), Declaration of Helsinki, and International Ethical Guidelines for Biomedical Research Involving Human Subjects, applicable national government regulations, and Institutional research policies and procedures. All investigators will receive GCP training to the onset of the study. Ethical approvals will be sought prior to commencement of the project from Thailand's Central Research

Ethics Committee and the London School of Hygiene & Tropical Medicine. The study protocol, informed consent form, participant's information sheet and other relevant information has been submitted to and approved by Chiang Mai University and local Ethics Committee. Any future amendments of the protocol shall be submitted to and approved by the Intuition Review Board (IRB) before implementation

## 11.2 CONSENT

As this is a cluster-randomised study, consent to randomisation is obtained at the cluster (hospital) level. Informed consent will be obtained for procedures that are specifically for the purposes of the study, i.e. data collection and blood tests for adults newly diagnosed with diabetes and for those with poor control within three years after diagnosis. Consent to enter the study must be sought from each participant only after a full explanation has been given, an information leaflet offered, and time allowed for consideration. The PI is responsible for ensuring that all vulnerable participants are protected and participate voluntarily in an environment free from coercion or undue influence. All information sheets and consent forms will be available in English and Thai and will be verified for accuracy through back-translation. Consent discussions will be conducted in the appropriate language and a translator will be used if necessary.

## 11.3 CONFIDENTIALITY

Any participants' identifiable data collected by the Study Coordination Centre will be stored securely and their confidentiality protected in accordance with the Data Protection Act 1998.

To protect against the possibility that personally identifiable information will be accessed and used by unauthorised individuals, several security measures will be applied. Data collection devices (laptops/tablets) will be password protected. Access to electronic data on servers located at CMU and LSHTM will be protected using access controls including password protection; access will only be available to research personnel through the authorization of the PIs. An audit trail will record activity on the main Access databases. All staff will be trained in handling of personally identifiable data. Qualitative and quantitative data will be anonymised at the earliest opportunity. Qualitative data will be used to inform intervention development and the process evaluation only; generic identifiers (e.g. participant 1) will be used from the transcription stage onwards. The key linking participants' names with study IDs will be stored separately from other data in a double-locked file at the secure project office, with access restricted to appropriate study personnel. Paper consent forms will be stored similarly. Study reports, such as aggregated data in progress reports, will not contain identifying information. Project office computers will be safeguarded from theft and damage (e.g. using locks, encryption, and antivirus software). Fully anonymised data may be transferred for analysis to co-investigators at LSHTM and other academic and commercial partners. A secure encrypted data transfer service will be used. Upon request, participant records will be made available to the study sponsor.

## 11.4 INDEMNITY

London School of Hygiene & Tropical Medicine holds Public Liability ("negligent harm") and Clinical Trial ("non-negligent harm") insurance policies, which apply to this trial.

## 11.5 SPONSER

London School of Hygiene & Tropical Medicine will act as the main sponsor for this study. Delegated responsibilities will be assigned locally.

## 11.6. FUNDING

The UK Medical Research Council and The Thailand Research Fund are funding this study.

## 11.7. AUDITS AND INSPECTIONS

The study may be subject to audit by the London School of Hygiene & Tropical Medicine under their remit as sponsor, the Study Coordination Centre and other regulatory bodies to ensure adherence to GCP.

# 12. TRIAL MANAGEMENT

## 12.1 TRIAL MANAGEMENT GROUP

The TMG will be responsible for overseeing the progress of the trial, and will meet monthly by Skype, and once each year in person, using opportunities afforded by existing collaborations and cross-appointments. Safety and adverse events will be reviewed at TMG meetings, and any concerns will be reported to the Trial Steering Committee (TSC), and their advice followed. The TMG will also formulate key policies and working groups (e.g. communication, data management, publication).

A Trial Management Group (TMG) will be formed, consisting of the following:

- Chief investigator
- Local Principal Investigators
- Other co-investigators
- Local project managers
- Local trial administrators

## 12.2 TRIAL MANAGEMENT COMMITTEE

The role of the Trial Steering Committee (TSC) is to provide overall supervision of the trial. The TSC will meet bi-monthly for the first year then every six months after that. The TSC will take responsibility for the following:

- Monitoring and supervision of the trial
- Review progress towards the study milestones
- Amending the protocol if needed
- Approve any additional trial sites
- Confirm all approvals are in place before the start of recruitment
- Advise the TMG on any safety concerns
- Oversee publication of trial results

The TSC will include experts in the field of DSME, health psychology and clinical trials, and will have an independent Chair. In addition, there will be patient and carer representatives as well as policy representation. [Membership to be confirmed]

## 12.3 DATA MONITORING AND SAFETY OVERSIGHT

A formal Data Monitoring Safety Board will not be convened, as there are minimal risks from this educational intervention and related data collection. If any adverse events are apparent then this will be reviewed and addressed through the regular TMG meetings and in consultation with local site guidelines.

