## STUDY SYNOPSIS

Type 2 diabetes is amongst the foremost challenges facing policy makers in Thailand, accounting for considerable death, disability and healthcare expenditure. Under Thailand's strong primary health system, medical management of diabetes is widely available. However, control of blood glucose and other cardiovascular disease risk factors, and regular screening for early detection of complications remain low due to a lack of services for education and counselling to support behavioural changes necessary for good self-management of the condition. A substantial literature documents the effectiveness of Diabetes Self-Management Education (DSME) programs for improving diabetes outcomes, although little high-quality data are available in Thailand, and traditional delivery models (health-professional led one-to-one or small-group sessions) are unlikely to be scalable in Thailand given current human resource and budgetary constraints. Thus, we propose to develop a low-cost DSME program and scalable delivery model for roll-out within the Thai primary care system.

The intervention is based on behaviour-change and social support theories. This will be delivered in monthly group meetings by lay health workers or nurses, and aided by a suite of short films to introduce key topics and stimulate discussion. We will randomise 21 primary care units to offer DSME to adults diagnosed newly diagnosed with type 2 diabetes and those with poor controlled type 2 diabetes diagnosed within the first three years. This will be delivered by lay health workers, nurses (for comparative effectiveness), or usual care. After 12 months, we will compare glycaemic control and cardiovascular risk scores between the three arms. We will conduct cost-effectiveness, process and policy evaluations to produce best-buy recommendations for the Thai Ministry of Public Health.

[figure not shown]
Through our 3-arm trial design, we will be able to compare effectiveness of nurse-, peer-delivered and standard care, and this along with the process evaluation will provide important lessons for the field of peer-delivery of interventions. In particular, questions remain whether peer educators can be easily trained to effectively deliver state-of-the-art behavioural counselling techniques based on a manualised intervention. The potential for peers to offer long-term support, which might better sustain behaviour change, is also untested and will be investigated through our process evaluation.

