Programs that are more effective usually offer more than 10 hours contact, incorporate behavioural approaches, and provide longer-term support mechanisms. Providing intensive and sustained support however has cost implications, resulting in ongoing efforts to identify more cost-efficient ways to deliver DSME, notably through digital technology (with variable effectiveness) and peers. Peers can support sustained changes in complex health behaviours by providing assistance in daily management, social and emotional support, linkage to clinical care, and ongoing availability of support. Unlike the educational/psychological framework of professional support, peer support operates on a social support framework. Although traditionally restricted to those with experience of disease, the definition of peers has been expanded to include other non-professionals with close relations to the community (e.g. community health workers). However, despite widespread interest, empirical data on effectiveness of peers in supporting behaviour change in chronic diseases, including diabetes, is limited and inconsistent. In an earlier review, the World Health Organisation did not find sufficient evidence to recommend peer support programs as a policy option for diabetes management in LMICs. Data on cost-effectiveness, acceptability and potential adverse consequences of peer support programs from diverse settings, as well as optimal strategies for mobilising and integrating peers in diabetes care pathways, are lacking.

Since the 1960s, community health workers (called village health volunteers) have been a regular part of the Thai healthcare system, linking communities with healthcare providers and providing a range of assistance and

outreach services. The presence of a nationwide network of community health workers (1 million) offers a unique opportunity to develop a scalable model of DSME provision, while building local capacity, and generating critical data on role of peer support programs in LMICs. Taking a similar approach, a multi-country demonstration project in 2010, successfully trained village health volunteers in Thailand for DSME delivery. The study authors reported a substantial engagement and acceptance of the program; however, clinical outcomes could not be robustly evaluated due to fieldwork challenges (before-after data were available for 53 participants only).

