## 2.2 RATIONALE

The health and economic consequences of Type 2 diabetes mellitus are largely attributable to its complications, which may be prevented or delayed through good disease control. This can be achieved through medical care and self-management. Diabetes Self-Management Education (DSME) programs are effective and cost-effective, and part of standard care in high-income countries, but are unavailable in Thai healthcare system, despite universal coverage of medical aspects of diabetes care. Negative perceptions of educational programs, sustained by a lack of high-quality local data, and concerns about burden on existing staff time and costs are thought to be responsible.

Given the focus on community-based education for chronic diseases in recent primary healthcare reforms, it is timely to scale-up DSME in Thailand, if an affordable model of delivery for a locally-tailored intervention can be found. Taking this opportunity, we propose to work in close collaboration with the Thai Ministry of Public Health to develop, pilot and evaluate a peer-based DSME program and delivery model, finally producing a list of policy recommendations for optimal integration into the Thai healthcare system. Participants will be free to drop into any number of meetings (full or partial) and encouraged to contact their nurse or village health volunteer for advice as necessary. While there is a theoretical risk that this could increase the cost of the program, it is anticipated that it will be regulated by the unwillingness of the participants to attend the program beyond its usefulness; identifying this potential unintended consequence will form part of our process evaluation.

The proposal is to develop a culturally tailored DSME program for Thailand and evaluate its clinical and cost-effectiveness under two alternative modes of delivery: nurse-led and peer-led. While the exact structure of the intervention will be determined by the formative research carried out under this proposal, a low-impact and sustained delivery model is most likely to achieve our twin objectives of long-term behaviour change and scalability.

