## 6.4 RISKS AND BENEFITS

No major ethical issues are expected since only interventions recommended in established recent guidance issued will be offered. By participating in the study, participants will not be denied any form of care that is currently available to them, subject to local provision of services. Participants may find minor discomfort from the taking blood samples. Trained phlebotomists will take the blood sample. Results of Interim blood test, that is not part of routine care, such as HbA1c will be fed back by the study team to health care professionals only if there is a need for additional clinical treatment/management. The information sheet will stress the independence of the research team and that all data will be anonymised

The Patient Information Sheet will provide potential participants with information about the possible benefits and anticipated risks of taking part in the study either as a participant in the main intervention or in the qualitative study. Participants will be given the opportunity to discuss any issues with their healthcare provider or researcher prior to consenting to participate. The researcher will inform the participant if new information comes to light that may affect the participant's willingness to participate in the study.

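### Adverse events are reviewed only if they come to notice, programme contact differs by arm, and no common-visit question makes event counts comparable across arms

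*Combined protocol and SAP*

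**What the plan says.** **How events reach review.** Section 12.3 gives the condition: "If any adverse events are apparent then this will be reviewed and addressed through the regular TMG meetings". It also declines a monitoring board: "A formal Data Monitoring Safety Board will not be convened, as there are minimal risks from this educational intervention". Section 12.1 says, without that condition, that the Trial Management Group (TMG) reviews adverse events at its meetings and refers concerns to the Trial Steering Committee. Neither section says how an event is found or recorded.

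**What is collected and analysed.** The Protocol Summary, sections 4.1.1, 8 and 9.2, and Table 1 list outcomes and data at baseline, 6 and 12 months. None includes an adverse-event item. Section 10.2.1 plans mixed models for outcome data and mentions no adverse-event analysis.

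**Contact by arm.** Study visits are the same in all arms (section 8). For the intervention arms the Study Synopsis adds: "This will be delivered in monthly group meetings by lay health workers or nurses". Section 2.2 makes attendance voluntary, with participants also "encouraged to contact their nurse or village health volunteer for advice as necessary". Section 7.1 leaves standard care unchanged, in units with a full-time nurse, a weekly doctor visit and 10-15 village health volunteers. It does not say how often patients are seen. Section 4.1 states that the trial is unblinded.

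**The evidence gap.** Section 2.1 lists the following as lacking: "Data on cost-effectiveness, acceptability and potential adverse consequences of peer support programs from diverse settings".

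**The concern.** When nobody is assigned to ask, an event is counted only if it surfaces at some contact. Programme contact is unequal by design, so two arms with the same true risk can produce different counts.

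Two distortions are possible, in different comparisons:

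- **Intervention against standard care.** The meetings give extra occasions for an event to be mentioned, so the intervention arms could show an excess that is only detection.
- **Peer against nurse.** Scheduled contact is similar, but one arm relies on a lay volunteer and the other on a nurse to recognise an event and pass it on. Under-recognition in the peer arm could look like safety.

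The second matters because the trial feeds a recommendation on which delivery model to scale (sections 3 and 13). Reported counts could neither support nor rule out a difference in harm. With no monitoring board, this passive route is the main safety mechanism described.

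**Working it through.** The plan states no safety figure, so there is none to reproduce. The sample size of 693 plays no part in this point and does not change with the fix.

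**Step 1: is there any route of elicitation?**

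| Place in protocol | What it covers | Asks about adverse events? |
|---|---|---|
| Protocol Summary; 4.1.1 | outcomes | no |
| 8; Table 1; 9.2 | interviews, blood samples, questionnaires, body measurements | no |
| 10.2.1 | quantitative analysis | no |
| 12.1 | TMG review and escalation | no collection method |
| 12.3 | review if apparent | no collection method |

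**Step 2: how much could unequal contact matter?** Let *p* be the chance that an existing event surfaces at any one contact, independently across contacts. With *k* contacts,

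P(detected) = 1 − (1 − p)^k.

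With equal true risk, the apparent ratio is

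[1 − (1 − p)^k_int] / [1 − (1 − p)^k_ctl].

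Inputs:

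- Study visits after baseline: 2 in every arm (section 8).
- Meetings: 12 in the intervention arms. This is an assumption: one a month over 12 months, all attended. The documents give no count.
- Routine contacts: *r*, the same in every arm, because section 6.4 says nobody loses existing care. The value is not given, so 0, 4 and 12 are tried.
- *p* = 0.10, an assumption.

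So k_ctl = 2 + r and k_int = 14 + r.

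- r = 0: (1 − 0.9^14)/(1 − 0.9^2) = 0.771/0.190 = 4.1
- r = 4: (1 − 0.9^18)/(1 − 0.9^6) = 0.850/0.469 = 1.8
- r = 12: (1 − 0.9^26)/(1 − 0.9^14) = 0.935/0.771 = 1.2

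**Step 3: sensitivity, by the same formula.**

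| p | r = 0 | r = 4 | r = 12 |
|---|---|---|---|
| 0.05 | 5.3 | 2.3 | 1.4 |
| 0.10 | 4.1 | 1.8 | 1.2 |
| 0.20 | 2.7 | 1.3 | 1.04 |
| 0.50 | 1.3 | 1.02 | 1.0 |

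With half the meetings attended (6) and p = 0.10, the ratios are 3.0, 1.5 and 1.1. With none attended, or with meetings replacing routine contacts one for one, k_int = k_ctl and the ratio is 1.

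The formula treats an event as open to detection at every contact. Events late in the year have fewer contacts left, so the figures show direction and range only.

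**Step 4: peer against nurse.** Contact counts are alike, so this formula shows no difference. Any bias comes from a lower *p* at volunteer-led meetings. The documents give nothing from which to set it, so it is left unquantified.

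**The case against.** The strongest reply is that this is oversight of a low-risk educational programme and not an endpoint. No between-arm adverse-event comparison is planned, and safety is not among the specific objectives. That stands. The point is therefore about what a comparison of spontaneously noted events could bear, and about harms that might be missed.

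Much that bears on harm is already measured on one schedule in all arms: anxiety and depression (HADS), perceived stress, quality of life, HbA1c and blood pressure. Section 7.1 adds prospective resource use, which may include hospital use although its items are not listed. It also adds a process evaluation that looks for unexpected mechanisms. These cover part of the gap named in section 2.1, so it would be wrong to infer that the gap stays wholly unanswered. They do not yield a defined, comparable adverse-event count by arm.

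Three other stronger readings are tempting and unsupported:

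- **That standard-care patients are seen only at study visits.** They keep routine nurse, doctor and volunteer contact. Setting 14 contacts against 2 describes only the limiting case of no routine contact and full attendance.
- **That any safety comparison would be distorted.** Measures taken at the common visits do not depend on programme contact for their collection, and the bias in spontaneous counts could be close to nil.
- **That section 6.4 contradicts section 2.1.** The former says "only interventions recommended in established recent guidance issued will be offered"; the latter reports that an earlier review "did not find sufficient evidence to recommend peer support programs as a policy option for diabetes management in LMICs". Section 2.1 also says most clinical guidelines recommend self-management education. Programme content and peer delivery as policy are different matters, so no conflict is shown.

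Finally, section 12.4 on local management was not in the text available for review, so local reporting arrangements cannot be presumed absent.

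**Conclusion.** The concern holds in a limited form. In the text available, adverse events are undefined, are not elicited at the common visits, and enter review only if noticed. With unequal programme contact and no blinding, spontaneously noted events would not be safely comparable across arms.

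The likely direction is over-detection in the intervention arms against standard care, with possible under-recognition in the peer arm relative to the nurse arm. These can pull the peer arm's count in opposite directions, so its net bias cannot be signed.

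The size is unknown. The range of about 4.1 to 1.2 rests on assumed values: 12 attended meetings, a 10% chance per contact, and 0 to 12 routine contacts added equally to every arm. It approaches 1 if meetings are unattended or replace routine contact, or if nearly every event surfaces anyway. No single false risk ratio should be quoted. The primary outcomes, sample size and power are unaffected. The change is worth making because it is cheap and the plan offers no substitute.

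**What to change.** In sections 8 and 12.3:

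1. Define an adverse event for this trial.
2. Have fieldworkers ask every participant in all three arms the same short, fixed question set at the existing 6- and 12-month interviews. The trial team should choose the items (hospital admission or emergency attendance would be examples) and align them with the resource-use items where these overlap, so nothing is asked twice.
3. Obtain deaths from the units in the same way in every arm, since an interview cannot capture them.
4. Record the source of each event: study interview, group meeting or other.
5. Tabulate interview-elicited events by arm, with the number asked in each arm as denominator. List events volunteered at meetings separately, for TMG review, and keep them out of the between-arm comparison.

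Identical questions remove the difference in opportunity to report. They do not remove imperfect recall over six months, loss to follow-up, or any greater readiness to report among participants who know their arm. The table should carry that caution.

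The cost is a few minutes per interview, one table and a protocol wording change, with no extra staff or visits.
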